1. Protocol Title

Effect of GOCOVRI on Quantity and Quality of Gait in Parkinson's disease

2. Objectives

Aim I: Investigate the effect of GOCOVRI™ on activity levels in people with Parkinson's disease (PD) and Levodopa induced dyskinesia (LID)

Hypothesis I: We hypothesize that GOCOVRI™ will result in an increase of daily activity due to improvement in LID symptoms.

Primary outcome measures: Total number of steps and turns per day

Aim II: Investigate the effect of GOCOVRI™ on comprehensive measures of gait and balance quality in people with PD with LID

Hypothesis II: We hypothesize GOCOVRI™ may improve discrete characteristics of gait and balance that is evident even within the first hour of the day walking.

3. Background

Levodopa induced dyskinesia (LID) is a symptom of Parkinson's disease for which there are limited treatment options. LID leads to reduced quality of life, increased caregiver burden and an increased risk of falls (Rascol et al., 2015, Chapuis et al., 2005). GOCOVRI™ is an extended release capsule prescription medication shown to reduce LID in people with PD (Pahwa et al., 2017, Pahwa et al., 2018). However, a number of studies have identified an increase in falls in those on the active medication study arm but not the placebo arm (13% increase in active and 7% in placebo) (Pahwa et al., 2017). In order to understand this increase in falls, comprehensive measurements of quantity of activity (gait measured in the home environment) and quality of activity (comprehensive gait characteristics that may increase risk of falls) need to be assessed in participants taking GOCOVRI™. In addition, the evidence for the effect of GOCOVRI™ on gait and balance in PD is limited (Smulders et al., 2016).

4. Study Design

This is an open label study in which the participants with PD will know they are taking medication and the experimenters will know which study visits and 7 days of monitoring are baseline, prior to taking GOCOVRI, and which study visits and 7 days of monitoring are after taking maximum dose of GOCOVRI after 5 weeks. Subjects will be given Amantadine extended release for purposes of this study.

5. Study Population

a. Number of Subjects

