Female participants of childbearing age will need to have a urine pregnancy test to screen for pregnancy before being given study drug, and will be asked to commit to contraception for the duration of the study. If a participant inadvertently becomes pregnant during the study, the study drug will be stopped immediately and they will be removed from the study.

d. Setting

Prior to the first study visit, participants will go to the OHSU outpatient Laboratory or a local laboratory for an assessment of renal function (unless this test has previously been completed with in the 30 days prior to the first study visit). If renal impairment (estimated glomerular filtration rate (eGFR) < 50 ml/min/1.73 m²) is found, subjects will be excluded from the study as impaired renal function can increase the chances of adverse reactions to the study drug.

Participants will have virtual study visits remotely using Zoom: at baseline (week 1; 4 visits) and the other after 4 weeks of GOCOVRI™ (week 6, after 2 weeks at their maximum dose; 4 visits). During the baseline period (week 1) and the last week of maximum dose GOCOVRI (week 5), the participants will wear a SmartSocks sensor system for up to 10 hours of their total waking time, and a Phillips Actiwatch 24 hours/day for 7 consecutive days. All visits will occur remotely using Zoom and will last approximately 1 hour. All participants will be tested in their 'ON' medication state.

e. Recruitment Methods

Primarily, participants are to be recruited from the OHSU Movement Disorders Clinic by [name]. In addition to this, we have a laboratory database of PD volunteers for which we have information on LID from previous studies (IRB# 7797) and for which [name] will assist in reviewing. Finally, neurologists in the OHSU Movement Disorders Clinics will be alerted to the study by [name] so they can refer suitable participants.

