In order to collect physical activity and gait data in the home environment, data collection will take place for 7 days following the baseline remote assessments at week 1 and the second remote assessments at week 6. Overall activity levels for the 7 days will be continuously collected (24h/day) via a single, wrist-worn monitor (**Figure 2A, Phillips Actiwatch**). The wrist monitor will aid in evaluating early morning activity levels, in case subjects do not immediately put on the sock sensors.

To determine gait quantity and quality during the day, patients will be asked to wear a SmartSocks sensor system (**Figures 2B & 2C**) for 7 consecutive days. The SmartSocks system consists of one SmartSock sensor on each foot, and a single Opal sensor around the waist. The SmartSocks and the waist Opal will be worn for at least 8 hours/day. At night, the sensors will be removed and placed in a docking station to charge. At the baseline visit, participants will learn how to wear and charge the SmartSocks system. Subjects will be asked to charge the sensors in the bedroom and to put them on within 10 minutes of waking in order to collect gait data from the first hour of their day, prior to taking their first dose of

levodopa. After finishing the 7 days, subjects will mail back the sensors and docking station using pre-paid US mailing boxes or the sensors will be picked up by a research assistant. When participants have reached the maximum dose of GOCOVRI at week 4, a SmartSocks sensor system will be sent back to the participant by US mail or dropped off by a research assistant for a second week of daily-life mobility monitoring. Participants will be asked to repeat the same procedures for this second week (Figure 1). Data will be uploaded to an OHSU approved secure server upon return of the devices. After return of the sensors the integrity of the data will be assessed and if there is less than 5h/day an 5 days of data, then subjects will be asked to repeat the 1 week of wearing the sensors.

Figure 2. Sensors for daily-life data collection: **A)** Phillips Actiwatch 2 for activity levels and **B)** SmartSocks for daily-life data collection / **C)** Lumbar Opal for activity quality.

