Aim II: We will also separately examine the first hour of sensor data recording each day to see the overnight effect of GOCOVRI™ on activity and balance/gait. We will undertake analyses to determine which of our metrics are significantly different during the first hour of the day between Week 1 (before GOCOVRI) and Week 6 (after GOCOVRI) groups with paired t-tests (if data appear normally distributed) or nonparametric Wilcoxon signed-rank (data not normally distributed). We expect to see a significant change in metrics related to activity level especially during the first hour of the day before the levodopa intake as some subject with PD may have difficulty in initiating walking during the first hour of the day. This result would indicate that GOCOVRI is also helping patients to overcome the difficulty in initially walking during the first hour of the day before the levodopa intake.

Finally, we will explore the opportunity to identify which metrics of gait and balance best relate to LID and the medication fluctuations throughout the day to further understand how LID affects mobility.

9. Privacy, Confidentiality, and Data Security

Subject privacy. Recruitment will take place over the telephone with the researcher in a private office. Consenting will occur during a remote meeting prior to the first study visit with only study team member(s) present. Likewise, during the remote visits only study team members will be present.

Data privacy. Upon consent, a subject ID# will be assigned for a subject and all data files will only have this number on it – the ID number will not contain any of the 18 HIPAA identifiers. The file containing the link between subject name and ID# will be maintained on an encrypted lab computer, in an electronic-access office, and file will only be accessible by study team members who need it. After test session, electronic data will be uploaded to our laboratory database and in a web-accessible REDCap database that is located on a secure OHSU server. Any paper files will be kept in electronic-access only lab offices.

10. Provisions to Monitor the Data to Ensure the Safety of Subjects

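### The primary outcome is a daily total of steps and turns, but Section 5.d limits sensor wear to 10 hours, so wear that follows the protocol need not yield a daily total

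*Combined protocol and SAP*

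**What the plan says.** All references are to the combined protocol and SAP.

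- **Section 2, Aim I**: "Primary outcome measures: Total number of steps and turns per day". The hypothesis is that "GOCOVRI™ will result in an increase of daily activity due to improvement in LID symptoms".
- **Section 5.d, Setting**: "the participants will wear a SmartSocks sensor system for up to 10 hours of their total waking time". The same sentence has the wrist Actiwatch worn round the clock for 7 days.
- **Section 6, Daily-life data collection**: gait quantity and quality come from the SmartSocks system. On duration: "The SmartSocks and the waist Opal will be worn for at least 8 hours/day". On the end of wear: "At night, the sensors will be removed and placed in a docking station to charge". On the start, participants are asked to "put them on within 10 minutes of waking in order to collect gait data from the first hour of their day". A separate threshold of 5 hours a day and 5 days decides whether the week is repeated. The Actiwatch is given overall activity level and early-morning activity; it is not named as a source of steps or turns.
- **Section 8**: Week 1 and Week 6 are compared by paired t-test or Wilcoxon signed-rank test. Steps and turns are listed both per day and per hour. No rule states which hours of the day are compared or what makes a day valid. The closing exploratory analysis concerns "LID and the medication fluctuations throughout the day".

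**The concern.** The outcome is named as a whole-day count, but one of the two wear instructions allows only part of the waking day to be recorded. Because wear starts at waking, a continuous 10-hour recording stops before the evening.

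This matters in this trial for three reasons. First, Section 8 expects more activity especially in the first hour of the day. If part of that were walking done sooner rather than additional walking, a count over the first 10 hours would rise while the daily total stayed the same. Second, Section 8 would read a rise as an increase in overall activity level, and a single-arm before-and-after comparison has no control group in which a timing shift would also appear. Third, a real gain in the evening would go unrecorded, and the exploratory analysis of fluctuations across the day would have no evening gait data.

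The problem is distinct from unequal wear between the two weeks. It remains when both weeks have identical wear.

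**Working it through.** The plan gives no figure to reproduce: no waking hours, activity profile, SD, alpha or power. The check sets the wear statements side by side and then sizes the gap under stated assumptions.

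**Compatibility of the wear statements.** Section 5.d requires at most 10 hours; Section 6 requires at least 8. Any duration from 8 to 10 hours satisfies both, so on duration they do not strictly conflict. Section 6 read alone (on at waking, off at night) implies wear through the evening. The two sections therefore allow anything from an 8-hour to a whole-day recording under the same outcome name.

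**Assumptions, not in the documents.** Waking day W of 15, 16 or 17 hours; one continuous block of wear from waking; the 10-hour limit applied; evening walking rate either equal to, or half of, the rate in the first 10 hours.

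**Share of steps inside the window, f.**
- Even activity: f = 10/W.
- Evening at half rate: f = 10/(10 + 0.5 × (W − 10)).

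**Share missed = 1 − f. Apparent change when a fraction s of daily steps moves from after hour 10 into the window = s/f**, with a true change of 0. **Loss of post-hour-10 walking that this shift requires = s/(1 − f).** With s = 5%:

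| W | Profile | f | Missed | Apparent change | Evening walking that must be lost |
|---|---|---|---|---|---|
| 15 | even | 0.667 | 33% | +7.5% | 15% |
| 16 | even | 0.625 | 37.5% | +8.0% | 13% |
| 17 | even | 0.588 | 41% | +8.5% | 12% |
| 15 | half | 0.800 | 20% | +6.25% | 25% |
| 16 | half | 0.769 | 23% | +6.5% | 22% |
| 17 | half | 0.741 | 26% | +6.75% | 19% |

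**Per-hour rates.** With 10 worn hours in both weeks, the numerator and denominator come from the same window, so the percentage change in steps per hour is again s/f. Dividing by worn hours corrects unequal wear but not a timing shift.

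**Missed gain.** At W = 16 with even activity, a true 20% increase confined to the hours after hour 10 is 0.20 × 0.375 = 7.5% of the day and would be recorded as 0%.

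**Wear from waking to bedtime.** Then f = 1, nothing is missed, and a pure timing shift changes the recorded total by 0%.

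**The case against.** The strongest reply is that Section 6 is the operative procedure and Section 5.d only a summary under Setting. No passage tells participants to take the sensors off after 10 hours. If Section 6 governs, wear runs to night and the bias disappears. That stands: the documents do not establish that evenings will be lost, only that a stated limit permits it. It does not remove the need to correct Section 5.d, because a participant or coordinator following it would record a partial day.

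Second, the evening is not unobserved altogether, since the Actiwatch runs 24 hours a day. That is correct, and it would allow a check on whole-day activity. But the plan does not use it for steps or turns, or as a check on the primary outcome.

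Third, no section predicts less walking in the evening. Section 8 expects more first-hour activity because some patients have difficulty starting to walk. Under the assumptions above, a 5% shift means giving up 12 to 25% of post-hour-10 walking, and movement from late to early morning lies inside the window and causes no bias. This also stands.

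A reader might go further and infer that the plan carries a false-positive rate far above 5%. With 12 pairs, an assumed two-sided 0.05 level and an assumed SD of change of 15%, an apparent +8% would be significant about 39% of the time. The documents do not support that as a property of the plan. It stacks an enforced limit, a single block of wear, a particular shift and an invented SD. It runs from 71% at SD 10% to 24% at SD 20%, and falls to about 28% at SD 15% if evening walking is at half rate (+6.5%).

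Finally, unequal wear between weeks could matter more: at a constant walking rate, 10 against 8 hours changes the count by 10/8 − 1 = 25%. That is a separate issue and does not answer this one.

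**Conclusion.** The point holds in a limited form. The named primary outcome is a daily total, while the wear limit in Section 5.d, combined with the start at waking in Section 6, allows a count covering only about the first 10 waking hours. Under the assumed waking days, that omits 33 to 41% of waking time, or 20 to 26% of steps if evenings are half as active.

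If the limit is applied and walking moves across hour 10, a 5% shift would appear as about +6% to +8.5%; an evening gain would be missed. Both are conditional on assumptions that the documents neither state nor rule out. The documents do not show that the day will in fact be truncated, that evening walking will fall, or that the test has any particular error rate.

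The correction should be made because it concerns the only named primary outcome and costs little before data collection, and because steps and turns not recorded cannot be recovered afterwards.

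**What to change.** **Preferred.** In Section 5.d, replace the 10-hour limit with wear from waking until bedtime, at least 8 hours a day. State the same in Section 6 and in the participant instructions. This matches what Section 6 already implies and makes the recorded count correspond to the outcome in Section 2. The cost is some extra hours of wear over the two monitoring weeks; battery life is not stated, so feasibility needs confirming.

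**If the limit must stay:**
1. Define the primary as steps and turns in one fixed window after waking, identical in both weeks.
2. Reconcile that window with the repeat-week threshold of 5 hours a day and 5 days in Section 6. A day with 5 hours of data can pass that threshold without filling a longer window, so state whether such days are analysed. Shortening the window is not free: at 16 waking hours with even activity, an 8-hour window turns a 5% shift into 5%/(8/16) = +10%, against +8% for 10 hours.
3. Limit the Aim I conclusion to that window rather than to daily activity.
4. Pre-specify the 24-hour Actiwatch data, which are already being collected, as a check on whether whole-day activity rose or only moved earlier.

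This route needs no extra wear, but it costs a narrower conclusion, possible loss of incomplete days and of hours outside the window, and one added supporting analysis.

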Subjects will provide informed consent during a screening visit, and then will be screened for orthostatic hypotension (by blood pressure test listed in exclusions above), renal function (if not already available) and a urinary pregnancy test (female participants of childbearing age ONLY). To rule out potential participants with orthostatic hypotension for people who don't already know they have this condition, we will send an automatic blood-pressure cuff to participant and blood pressure will be checked during start of first virtual visit. We will explain how to place the cuff on arm and do the test themselves or with assistance of caregiver. Participants will take blood pressure while lying down after 5 minutes and then stand and repeat measurements at 2 and 5 minutes of standing. Orthostatic hypotension is defined as a drop of ≥ 20 mm HG systolic and ≥ 10 mm HG diastolic at 2 or 5 minutes of quiet standing after 5 minutes of supine rest. After confirming eligibility for study, the virtual visit will completed during which, subjects will be taught how to wear and charge the inertial sensors at home (SmartSocks sensor system) on the feet and belt for 7 days, as well as an activity watch (Phillips Actiwatch) worn on one wrist. They will be instructed on how to return the sensors by mail in a prepaid postal service box provided by the study. At the first study visit, subjects will then have a neurological exam to assess LID and PD severity and exclusion/inclusion criteria, followed by balance assessments using body-worn inertial sensors. After a total of 4 weeks on medication, subjects will repeat clinical, orthostatic hypotension test, and gait testing during the second study visit, followed by another week of daily-life monitoring (**Figure 1**).

[figure not shown]

Figure 1. Study protocol. Participants will initially be screened followed by a balance laboratory visit and 7-day gait assessment in the home. Following a 4-week titration to maximum dose, participants will take GOCOVRI™ at the maximum dose for 2 weeks before a second assessment and set of daily-life gait collection (week 6). A two-week titration to reduce medication intake will then follow until week 8.

Drug dosage

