We will use an open-label trial design in which 12 participants will be given GOCOVRI™ provided by Adamas Pharmaceuticals, Inc. [name] (PI) will sign the medication order and prescribe the doses and the medication will be administered by the OHSU research pharmacy. A research coordinator will pick up the medication from the pharmacy prior to the baseline study visit to give to the subject with instructions about when to start taking the medication and how to increase dose over time. The drug will be administered orally once daily before bedtime. A forced four-week titration will be prescribed with the active treatment arm receiving 137mg/day (2 pills) during weeks 2 and 3 which will be increased to 274mg/day (4 pills; unless dyskinesia is relieved by the lower dose; then will stay at initial dose – increase will be based on clinical response to the lower dose) for weeks 4, 5 and 6 (see Figure 1). Participants will be contacted by a research assistant after the dosage is increased to ensure there are no issues, which if reported will be followed up by [name]. In addition, participants will be encouraged to call a study team member if they are having difficulty tolerating the medication at any point during the study. If the subjects experience side-effects at higher dose, then they will be asked to continue at the 137mg/day until after the second assessment, then tapered off in a single week. If patients wished to continue on GOCOVRI we will reach out to their provider and share their interest in wanting to remain on the medication. It will be explained to patients that they will only be guaranteed to receive GOCOVRI during the course of the study and future use will be at their and their provider's discretion with cost as determined by their individual insurance and pharmacy providers.

Data collection

Prior to the first study visit, participants will go to the OHSU outpatient Laboratory or a local laboratory who will assess renal function (unless this test has previously been completed with in the 30 days prior

to the first study visit). If renal impairment (estimated glomerular filtration rate (eGFR) < 50 ml/min/1.73 m²) is found, subjects will be excluded from the study, and the subjects will be informed of the results and the results will be sent to their primary care physician. Subjects will complete a blood pressure test for orthostatic hypotension (OH). If OH is found, the person will be excluded from the study.

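### If the second home recording is in week 6, a repeat week falls almost wholly in the dose taper; the taper trigger for participants reduced for side effects is also ambiguous (low severity, cheap to fix)

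*Combined protocol and SAP*

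**What the plan says.** **Dosing.** Section 6, Drug dosage, gives 137 mg/day (2 pills) in weeks 2 and 3 and 274 mg/day (4 pills) in weeks 4 to 6. "The drug will be administered orally once daily before bedtime". The Figure 1 caption adds: "A two-week titration to reduce medication intake will then follow until week 8". For participants with side effects at the higher dose there is a separate rule: "they will be asked to continue at the 137mg/day until after the second assessment, then tapered off in a single week". Participants kept at 137 mg/day because it relieved their dyskinesia have no such rule.

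**Second home recording.** The timing differs by section:

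- Section 6, opening text: "gait testing during the second study visit, followed by another week of daily-life monitoring".
- Section 6, Daily-life data collection: "data collection will take place for 7 days following the baseline remote assessments at week 1 and the second remote assessments at week 6".
- Figure 1 caption: two weeks at maximum dose "before a second assessment and set of daily-life gait collection (week 6").
- Section 5d, Setting: "the last week of maximum dose GOCOVRI (week 5), the participants will wear a SmartSocks sensor system".

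**Repeat rule.** Daily-life data collection says that data are checked once the sensors are back. If there are too few hours or days, the participant wears them for another week. No timing is given for that week and nothing is said about dose.

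**Analysis.** Section 8 compares Week 1 with Week 6 by paired t-test or signed-rank test. It has no rule for recording days on a reduced dose.

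**The concern.** Steps and turns per day are the Aim I primary outcomes and come from this home week. The Aim II first-hour analysis uses the same recording to look for an overnight effect of a bedtime drug. Days recorded during a taper would enter both analyses as if they were on-treatment days.

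There are two routes. The repeat week can affect any participant whose first attempt is short of data. The reduced-dose rule can affect only participants who had side effects, so any contamination by that route would not be random. With 12 participants, each carries 1/12, about 8%, of the mean paired change.

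**Working it through.** The plan gives no figure to reproduce. The check is a day count.

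**Inputs**

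- Study weeks are 7 days, so week 5 ends on day 35 and week 6 on day 42.
- Stable dosing runs to the end of week 6 (Drug dosage), and the taper follows until week 8 (Figure 1 caption).
- With bedtime dosing, the dose on the evening of day d acts on day d+1. The last stable dose, on day 42, covers day 43.
- E is the last day of the second recording: 42 for a week 6 recording, 35 for a week 5 recording.
- g is the number of days for sensor return and data checking. The plan does not give it, so it is assumed.
- s is the recording day on whose evening the first reduced dose is taken (s = 0 is the evening before recording starts). The plan does not give it, so it is assumed.

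**(a) Repeat week, any participant.** The repeat occupies days E+1+g to E+7+g. Stable-dose days are those up to day 43:

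stable days = min(7, max(0, 43 − E − g))

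| Second recording | g = 0 | g = 1 | g = 3 | g = 7 |
|---|---|---|---|---|
| Week 6 (E = 42): max(0, 1 − g) | 1 | 0 | 0 | 0 |
| Week 5 (E = 35): min(7, max(0, 8 − g)) | 7 | 7 | 5 | 1 |

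A repeat wholly on stable dose needs 43 − E − g ≥ 7, that is E ≤ 36 − g. For g = 3 the recording must end by day 33 and so start by day 27. The maximum dose starts on day 22, so only 5 bedtime doses (days 22 to 26) would precede it. A recording starting on day 36 follows 14 (days 22 to 35), the two weeks at maximum dose that the plan intends. Moving the recording earlier therefore costs time at full dose.

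**(b) Reduced-dose rule, side-effect group only.** Take the recording as days 1 to 7 after the second visit, and the taper as free to start at any time after that visit:

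affected days = max(0, 7 − s)

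| s | Affected | Left if those days are excluded |
|---|---|---|
| 0 | 7 | 0 |
| 1 | 6 | 1 |
| 4 | 3 | 4 |
| 7 or later | 0 | 7 |

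If the taper follows the caption's order, or the recording is in week 5, the count is 0 of 7.

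**The case against.** **On (b), the case against is strong.** The protocol often calls the home week an assessment: in the Figure 1 caption for baseline, in the diary paragraph, and in Table 1, which has rows for both a final and a home assessment 2. Reading the second assessment to include the home week is therefore ordinary usage here. The caption puts down-titration after the collection. Section 5d has the recording in week 5, and the sensors go out once maximum dose is reached at week 4. Section 4 treats visits and monitoring as one post-treatment block. The trigger sets an earliest time for the taper and does not order a start. Figure 1 itself is not shown and may settle the sequence.

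Most of that stands, and overlap was probably not intended. What remains is that the caption also lists the second assessment and the home collection as separate items, that its taper is the two-week one, and that nothing in Drug dosage makes the one-week taper wait for the recording.

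**On (a),** the plan does not date the repeat or say that tapering proceeds while one is pending, and the caption's order could be stretched to cover a repeated collection. That is fair. But stable dosing is written to end with week 6 and the taper to finish by week 8, and no text holds the dose for a repeat.

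**Stronger readings.** A reader might infer that the protocol schedules tapering during the primary-outcome week, that everyone on 137 mg/day is exposed, or that the treatment effect is biased by a calculable amount. The documents support none of these. The first needs one reading of an ambiguous term, the second overlooks the participants kept at 137 mg/day because it worked, and the third needs numbers the plan does not give.

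**Conclusion.** The point holds as a low-severity inconsistency.

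- **Repeat week.** With a week 6 recording, the stated dosing calendar and repeat rule leave at most 1 of 7 stable-dose days for any participant, and none once turnaround takes a day. With a week 5 recording the count is 5 of 7 at an assumed 3-day turnaround. This does not depend on what the second assessment means.
- **Reduced-dose rule.** For participants moved to 137 mg/day because of side effects, the wording allows anywhere from 0 to 7 affected days, with 0 the likelier intention.

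Both counts rest on the assumed s and g and on a bedtime dose acting the next day. How many participants would need a repeat or follow the reduced-dose route is unknown and may be none.

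**What to change.** 1. Give one week for the second recording, the same in section 5d, section 6 and the Figure 1 caption, preferably early enough that sensor return and a repeat fit before week 6 ends. Weigh this against time at maximum dose: a week 5 recording starts after one week at that dose, and a full repeat then fits only if turnaround is 1 day or less.
2. Reword Drug dosage so that every participant, if tolerated, stays on their current dose until the second 7-day home recording and any required repeat are complete, and the taper starts only then. This is the main fix. The tolerability clause leaves the investigator free to taper earlier for safety.
3. Add to section 8 that any day following a reduced GOCOVRI bedtime dose is excluded from the Week 6 steps and turns values. Use the medication diary, with the bedtime GOCOVRI dose entered in it. This is a backstop only, because it leaves 1 day for s = 1 and 4 days for s = 4.

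**Cost.** A few sentences and no new visits. Some participants stay longer on a dose they tolerate, and a small extra supply must be dispensed in advance. Where the taper would otherwise have started straight after the visit, the side-effect group has about one more week (7 × 2 = 14 pills). With a week 6 recording and an assumed 3-day turnaround, every participant waits about 3 days (3 × 2 = 6 or 3 × 4 = 12 pills). A repeat makes that about 10 days (20 or 40 pills).
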